2.5.3 Handling of intercurrent events

The two intercurrent events of interest, treatment discontinuation, and treatment interruption, will be handled the same, as the statistical analysis of the primary estimand will include all patients, regardless of whether a patient had a treatment discontinuation or interruption. However, if 3 or more (approximately 10%) patients from the Evaluable Set have experienced the considered intercurrent event, a supplementary analysis for the primary estimand will be conducted taking into account the following.

- 1. Statistical analysis of the primary estimand after removal of subjects with treatment discontinuation for any reason
- 2. Statistical analysis of the primary estimand after removal of subjects with treatment interruption causing the total infusion time > 4 h and 20 minutes for any reason.
- 3. Statistical analysis of the primary estimand after removal of subjects with either treatment discontinuation or interruption for any reason.

2.5.4 Handling of missing values not related to intercurrent event

There will be no replacement of missing data not related to intercurrent events.

2.5.5 Sensitivity analyses

The time course of the relative percent change from pre-dose to each time point will be tabulated. A Mixed Model Repeated Measures (MMRM) will be fitted to assess the whole-time course.

As a sensitivity analysis, a MMRM will be fitted with the relative percent change from pre-dose potassium value as dependent variable, and pre-dose potassium value, actual treatment volume, duration of infusion, timepoint, and actual treatment volume by timepoint interaction as covariates. This model implicitly imputes missing values by means of the estimated parameters and provides unbiased estimates for the data which are missing at random (MAR). Least-Squares Means and their 95% confidence intervals will be presented by timepoint and overall. A general (unstructured) variance-covariance matrix for the repeated measures for a single patient will be used.

This analysis will be repeated for absolute change from pre-dose.

Absolute change and relative percent change from pre-dose will be plotted against time to visualize the trend (increasing or decreasing) over time.

Advanced Accelerator Applications,	Confidential	Page 16 of 27
A Novartis company		
SAP amendment		CAAA001A12401

2.5.6 Supplementary analyses

Potassium level measured on whole blood does not account for potential hemolysis and thus may overestimate the actual level of potassium that would have been measured in serum. A supplementary descriptive analysis, similar to the primary analysis, including all post-infusion potassium levels, irrespective of the sample source, will be conducted to assess whether the increase in potassium is still acceptable despite the expected overestimation. Patients with pre-treatment potassium level measured in whole blood will be excluded from this analysis.

For the potassium levels measured at pre-infusion and any post-infusion time points, regardless of sample sources, categories based on normal range and Common Toxicity Criteria (CTC) grade will be summarized across the Safety Set at each time point to assess the frequency of elevated potassium levels.

To further assess the effect of LysaKare[®] infusion over a 24-hour period, the change in the other electrolyte and blood gas components post-infusion (Sodium, Chloride, pH, Lactate, CO_2 , and HCO_3) will be analyzed. The primary analysis will be repeated for these parameters.

The primary analysis will be repeated for subgroups of interest described in Section 2.2.1.

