Confidential

	In order to calculate the sample size for the study, initially a requirement was chosen that the length of the 95% confidence interval of the mean change from baseline to 4h does not exceed 0.2 mmol/L at an observed historical standard deviation of 0.3. With a targeted minimum of 25 subjects evaluable for this endpoint, the length of this confidence interval is maintained with a slight increase to 0.25 mmol/L. The safety data analysis will be presented with special focus on LysaKare [®] related treatment emergent events and will be applied to the full Safety Set. Changes in Vital Signs and ECG will be summarized by time. Changes in laboratory parameters (Haematology and Blood Chemistry) will be described by time.
Key words	LysaKare [®] , amino acid, GEP-NET, PRRT, Lutathera [®]

Advanced Accelerator Applications Clinical Trial Protocol (Version 01)

Confidential

Version history

Version Number	Description
Global protocol v00 dated 12-Nov-2019	Initial global protocol. Approved in all countries.
Local protocol v00 PL.01 dated 18-May-2021	Local amended protocol from v00. Approved in Poland
Global protocol v01 dated 01-Dec-2022	Amended global protocol from v00 and local protocol v00-PL.01 dated 18-May-2021

Protocol Amendment 01

As of 08 November 2022, 30 patients were enrolled into the study and received an infusion of LysaKare[®].

Amendment rationale

The primary purpose of this amendment is to provide clarification on the sampling requirements for laboratory assessments. The Sponsor identified discrepancies in sampling used for electrolytes which were not performed as per protocol requested procedures. This resulted in samples collected with heparinized blood (2 patients) and whole blood (11 patients) instead of serum sampling across 4 sites. Therefore, the Visit Schedule and assessments in Section 8 have been updated to clarify the requirements of laboratory assessments.

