Furthermore, as the potassium levels measured in serum differ from those measured in the heparinized blood or whole blood, the discrepant measurements cannot be used for the assessment of the primary endpoint "change in serum potassium levels at specified time points after LysaKare[®] IV administration compared to baseline." Therefore, the target enrollment number has been revised from "40" to "approximately 45" to ensure at least 25 patients have valid data to fulfill the study primary objective, which is to assess the effect of LysaKare[®] administration on serum potassium concentrations in GEP-NET patients eligible for Lutathera[®] treatment. For those participants with potassium levels not measured in serum, other collected data (e.g. AEs, ECG, other laboratory tests) will still be used to assess the secondary endpoint "to confirm the safety profile of LysaKare[®] infusion in GEP-NET patients eligible for Lutathera[®] treatment without co-administration of Lutathera[®]."

This protocol amendment also incorporates the changes made in Poland local protocol amendment v00-PL.01 dated 18-May-2021.

Advanced Accelerator Applications Clinical Trial Protocol (Version 01)

Confidential

Changes to the protocol

- Protocol synopsis, Section 3 Study Design, Section 6 Treatment: revised from 40 patients to approximately 45 patients (to have at least 25 evaluable for the primary endpoint).
- Protocol synopsis, Section 3.1 Screening phase, Section 3.2 Treatment phase, Exclusion criteria #1: For Poland only, added required hyperkalemia level > 5.5mmol/L per local protocol amendment.
- Section 3.2 Treatment phase, Section 4.3 Risks and benefits, Section 6.3.2 Dose discontinuation: Added text "in the occurrence of severe renal insufficiency referral to hemodialysis unit should be considered per investigator discretion."
- Table 8-1: Updated to clarify the requirements for chemistry and electrolyte testing using serum, for venous blood gas and antiemetic administration. Added text: The same sampling methodology should be used at all time points for consistency. **Before "LysaKare® infusion, an intravenous bolus of an antiemetic should be given. The choice of antiemetic drugs is at the discretion of the physician."
- Section 8.4.2 Laboratory Assessments: Added text detailing the tests and time-points where serum sampling is required. Added text "Samples must be processed and analyzed as soon as possible to avoid degradation."

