2.5.2 Statistical hypothesis, model, and method of analysis

The study is descriptive in nature, and no hypothesis will be tested for study endpoints. The study will analyze and describe various parameters related to serum potassium concentration,

Advanced Accelerator Applications,	Confidential	Page 15 of 27
A Novartis company		
SAP amendment		CAAA001A12401

including mean change, maximum change, and time to the maximum change. In particular, maximum change and time to the maximum change will be summarized by descriptive statistics (N, median, minimum, maximum, and interquartile range).

The mean (+/- SD) concentration-time profiles for serum potassium concentration by treatment over time will be displayed graphically for the Evaluable set on the linear view.

To visualize the evolution of potassium level for each patient a spaghetti plot will be displayed along with a box plot to see the summary of potassium levels at each time point.

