2.7.3 Laboratory data

On analyzing laboratory data, data from all sources will be combined. The summaries will include all assessments available for the lab parameters collected no later than 24 hours after the start of the LysaKare[®] infusion. The laboratory parameters that will be investigated, and the timing that the laboratory parameters will be assessed are summarized in Table 2-1.

	ematology and Chemist		incitta
Haematology (Assessment at screening, pre-dose and 24h after start of the infusion)	Blood Chemistry (serum) (Assessment at screening, pre-dose and 24h after start of the infusion)	Electrolytes (serum) (Assessment at screening, pre-dose and 2h, 4h, 6h, 8h, 12h and 24h after start of the infusion)	Venous Blood Gas (Assessment at screening, pre-dose and 2h, 4h, 6h, 8h, 12h and 24h after start of the infusion)
WBC with differential	BUN or urea	Potassium	рН
Platelets	Uric acid	Sodium	Lactate
Haemoglobin	Serum creatinine	Chloride	pCO2
Haematocrit	Creatinine clearance* Albumin Total bilirubin Alkaline phosphatases AST/ASAT ALT/ALAT	HCO3	
	Gamma-GT		
	Glucose		
	LDH		

Table 2-1 Hematology and Chemistry Laboratory Assessments

(*) Calculated using Cockcroft-Gault formula

Laboratory values outside normal ranges will be listed and flagged. The following flags will be used:

'+': 'Higher than reference value'

'-': 'Lower than reference value'

The respective parameter and the flagged value will be presented patient-wise by visit together with the reference values.

Advanced Accelerator Applications,	Confidential	Page 19 of 27
A Novartis company		
SAP amendment		CAAA001A12401

The following summaries will be produced for hematology and biochemistry laboratory data (by laboratory parameter and treatment):

- Worst post-baseline Common Toxicity Criteria (CTC) grade (regardless of the baseline status). Each subject will be counted only for the worst grade observed post-baseline.
- Shift tables using CTC grades to compare baseline to the worst on-treatment value.
- For laboratory tests where CTC grades are not defined, shift tables using the low/normal/high/(low and high) classification to compare baseline to the worst on-treatment value.

The following listings will be produced for the laboratory data:

- Listings of all laboratory data, with CTC grades and classification relative to the laboratory normal range. Lab data collected during the post-treatment period will be flagged.
- Listing of all CTC grade 3 or 4 laboratory toxicities.

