5.3 Laboratory parameters derivations

Grade categorization of lab values will be assigned programmatically as per National Cancer Institute (NCI) CTCAE version 5.0 or more recent version. The calculation of CTCAE grades will be based on the observed laboratory values only, clinical assessments will not be taken into account. The criteria to assign CTCAE grades are given in Novartis internal criteria for CTCAE grading of laboratory parameters. The latest available version of the document based on the underlying CTCAE version 5.0 or more recent version at the time of analysis will be used (refer to Table 5-3 in the Novartis internal criteria for CTCAE grading of laboratory parameters). For laboratory tests where grades are not defined by CTCAE v5.0 or more recent version, results will be graded by the low/normal/high classifications based on laboratory normal ranges.

A severity grade of 0 will be assigned for all non-missing lab values not graded as 1 or higher. Grade 5 will not be used. For laboratory tests that are graded for both low and high values, summaries will be done separately and labelled by direction, e.g., sodium will be summarized as hyponatremia and hypernatremia.

Imputation Rules

CTC grading for blood differentials is based on absolute values. However, this data may not be reported as absolute counts but rather as percentage of WBC.

If laboratory values are provided as '<X' (i.e. below limit of detection) or '>X', prior to conversion of laboratory values to SI unit, these numeric values are set to X.

Advanced Accelerator Applications,	Confidential	Page 26 of 27
A Novartis company		
SAP amendment		CAAA001A12401

The following rules will be applied to derive the WBC differential counts when only percentages are available for a xxx differential,

xxx count = (WBC count) * (xxx %value / 100)

Further derivation of laboratory parameters might be required for CTCAE grading. For instance, corrected calcium can be derived using the reported total calcium value and albumin at the same assessment using the following formula:

Corrected Calcium (mg/dL) = Calcium (mg/dL) - 0.8 [Albumin (g/dL)-4]

In order to apply the above formula, albumin values in g/L will be converted to g/dL by multiplying by 0.1), calcium values in mmol/L will be converted to mg/dL by dividing by 0.2495. For calculation of laboratory CTC grades 0 and 1, the normal range for derived corrected calcium is set to the same limits (in mg/dL) as for calculation.

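### The only by-time-point table of raised potassium pools serum, whole-blood and heparinised values, so it cannot separate true elevation from sampling artefact

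*SAP*

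**What the plan says.** SAP 2.5.6 plans two supplementary potassium analyses that use non-serum samples.

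- **Frequency table.** At each time point, for pre-infusion and post-infusion values alike, "regardless of sample sources, categories based on normal range and Common Toxicity Criteria (CTC) grade will be summarized across the Safety Set". Its stated aim is to show how often potassium is raised.
- **Mixed-source change analysis.** This repeats the primary description of change with post-infusion values from any source. It carries one exclusion: "Patients with pre-treatment potassium level measured in whole blood will be excluded from this analysis".

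The same section warns that a whole-blood measurement "may overestimate the actual level of potassium that would have been measured in serum". The rationale for Protocol Amendment 01 goes further, "as the potassium levels measured in serum differ from those measured in the heparinized blood or whole blood", and for that reason bars the discrepant values from the primary endpoint. It also gives the extent: "This resulted in samples collected with heparinized blood (2 patients) and whole blood (11 patients) instead of serum sampling across 4 sites". At that date 30 patients had been treated.

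On grading, SAP 5.3 says: "The calculation of CTCAE grades will be based on the observed laboratory values only, clinical assessments will not be taken into account".

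**The concern.** The purpose of this safety study is the effect of the infusion on potassium. The mean change is analysed in serum, but how often potassium is raised, and to what grade, is shown over time only in the pooled table. A CTC grade depends on the absolute level, so a falsely high whole-blood value is graded as if it were a true elevation.

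The two analyses in SAP 2.5.6 are also treated unevenly. The mixed-source change analysis has a serum counterpart, the primary analysis, against which it can be read. The frequency table has none. A reader of the study report could not tell how much of any count came from the specimen.

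**Working it through.** **Step 1. Is there a serum-only count by time point elsewhere?** The planned potassium outputs are:

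| Place | Output | Counts of raised values? | By time point? | Explicitly serum only? |
|---|---|---|---|---|
| SAP 2.5.2 | Mean, maximum and time of maximum change; plots | No | Yes (plots) | Part of the serum primary analysis |
| SAP 2.5.5 | Percent and absolute change; MMRM | No | Yes | Sensitivity to the primary analysis |
| SAP 2.5.6 | Normal-range and CTC categories | Yes | Yes | No, all sources |
| SAP 2.7.3 | Worst grade; shift to worst value | Yes | No | Not stated |
| SAP 2.7.1.1, 5.4.2 | Hyperkalaemia as AE of special interest; event rate with exact CI | Yes | No | Not stated |

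The plots come nearest: "a spaghetti plot will be displayed along with a box plot to see the summary of potassium levels at each time point". They let serum levels be seen, but they give no counts. SAP 5.4.2 does not define its hyperkalaemia event. SAP 2.7.1.1 searches by AE terms, and Protocol 10.1.1 makes an abnormal value an AE only under conditions such as symptoms or judged clinical significance. So no serum-only table by time point is planned.

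**Step 2. How many patients are involved?** Taking the two groups in the amendment rationale as different patients, 2 + 11 = 13.

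- At the amendment: 13/30 = 43%.
- At about 45 treated, if no more occur: 13/45 = 29%, leaving 45 − 13 = 32 with serum.

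**Step 3. Illustration at 4 h.** The documents give no size for the offset, so this shows scale only.

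- From the documents: historical mean level at 4 h of 4.2 + 0.9 = 5.1 mmol/L; 11 whole-blood patients; about 45 treated.
- Cut-off: 5.5 mmol/L, the Polish screening limit. It is a stand-in, because the documents do not list the table's grade limits.
- Assumed: SD of the level 0.4 (0.3 and 0.5 as alternatives); offset d = 0.2 to 0.5 mmol/L in all 11 whole-blood patients at 4 h; none in the 2 heparinised patients; normal distribution; no missing samples.

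Formula: pooled share = (34·s + 11·w)/45, where s = P(N(5.1, SD) > 5.5) and w = P(N(5.1 + d, SD) > 5.5).

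At SD 0.4, s = 0.1587.

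- d = 0.2: w = 0.3085; (34 × 0.1587 + 11 × 0.3085)/45 = 19.5%.
- d = 0.5: w = 0.5987; (34 × 0.1587 + 11 × 0.5987)/45 = 26.6%.

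| Assumed SD | No offset | Pooled, d = 0.2 | Pooled, d = 0.5 |
|---|---|---|---|
| 0.3 | 9.1% | 13.1% | 22.3% |
| 0.4 | 15.9% | 19.5% | 26.6% |
| 0.5 | 21.2% | 24.4% | 30.2% |

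In patients at SD 0.4, the expected excess is 11 × (0.3085 − 0.1587) = 1.6 to 11 × (0.5987 − 0.1587) = 4.8 of 45. With 6.0 mmol/L as the cut-off and SD 0.4, the share goes from 1.2% to between 1.9% and 4.8%.

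**Step 4. Heparinised baselines (side note).** If the exclusion does not cover them, the 2 known patients enter the mixed-source change analysis with a baseline offset of assumed size h = 0.2 to 0.5 mmol/L. With 32 serum patients the mean change shifts by 2h/34 = 0.012 to 0.029 mmol/L. With the minimum of 25 evaluable it shifts by 2h/27 = 0.015 to 0.037 mmol/L. The sign is unknown, and the shift is zero if the later samples carry the same offset.

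**The case against.** The pooling is declared, and the SAP states its expected direction. The table is supplementary, the study is descriptive, and no decision rule is attached to the table. An overcount is the cautious error in a safety study. The offset and level SD in the illustration are assumed. The SAP's mechanism is possible haemolysis, which need not affect every sample, and the amendment does not say that every sample of the 13 patients was non-serum. Normal ranges are local, so a site that supplied a specimen-specific range would partly correct the normal-range half of the table. All of this stands, and it limits the weight of the point. It does not supply the missing serum count, and the CTC half depends on the observed value.

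Four stronger readings are tempting, and the documents do not support them.

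- **A reader might infer that the plan has no serum-only frequency of any kind.** SAP 2.7.3 says "On analyzing laboratory data, data from all sources will be combined", which may mean laboratories or specimens, and its Table 2-1 lists potassium under serum electrolytes. The worst-grade and shift tables are therefore ambiguous on source. The claim is secure only for tables by time point.
- **A reader might bound the artefact by placing all 13 non-serum patients below or above a cut-off.** If 5 of 32 serum patients exceed it, the pooled share runs from 5/45 = 11.1% to 18/45 = 40.0%. That range includes ordinary differences between patients, so it does not bound the artefact.
- **A reader might infer that the pooled table must overcount.** The SAP says only that whole blood may overestimate, and neither document gives a direction for heparinised blood.
- **A reader might take the whole-blood baseline exclusion as a further fault.** It is a deliberate and conservative choice and can stand.

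**Conclusion.** The point holds as a worthwhile correction to a supplementary output. Both documents say that non-serum potassium is not equivalent to serum, at least 13 of the first 30 treated patients are affected, and the only table of raised potassium by time point mixes the sources with no serum version beside it. Following the plan as written gives a frequency that cannot be interpreted cleanly.

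The error is probably upward for whole blood and of unstated direction for heparinised blood. Its size is not known. The rise of about 4 to 11 percentage points at 5.5 mmol/L (19.5 − 15.9 = 3.6; 26.6 − 15.9 = 10.7) depends on the assumed SD of 0.4, the assumed offset, and a screening limit used as a cut-off.

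It should not be inferred that the primary result is compromised: the analysis of mean change uses serum on the Evaluable Set and is unaffected. The heparinised-baseline question is minor: two known patients, and about 0.04 mmol/L or less under the assumed offsets.

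**What to change.** In SAP 2.5.6:

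1. Report the normal-range and CTC-grade potassium frequencies at each time point for serum values first, with the number of serum values at that time point as the denominator.
2. Keep the all-source Safety Set table as supportive.
3. Show the number of patients by sample type (serum, whole blood, heparinised) at baseline and at each later time point.
4. For the mixed-source change analysis, state whether the whole-blood baseline exclusion also covers heparinised baselines.

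The cost is some SAP wording and one extra table with sample-type counts, from data already collected. Precision falls a little. Exact 95% intervals at a similar observed share are 5.3–32.8% for 5/32 (width 27.5 points) and 6.5–29.5% for 7/45 (23.0 points). At the minimum of 25 evaluable patients, 4/25 gives 4.5–36.1% (31.6 points). If heparinised baselines are excluded, the mixed-source change analysis loses up to two known patients. No primary analysis and no clinical rule changes.

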2.6 Analysis supporting secondary objectives

The secondary objective is to confirm the safety profile of LysaKare[®] infusion in GEP-NET patients without co-administration of Lutathera[®]. Further discussion of the safety endpoints to support the secondary objective analysis is seen in Section 2.7.

No efficacy endpoints will be assessed in this study.

2.7 Safety analyses

All safety analyses will be based on the safety set.

2.7.1 Adverse events (AEs)

All AEs, whether or not spontaneously reported by the patient, will be recorded starting from the signing of the ICF until the end of the Follow-Up phase. Any SAEs experienced after the 2-day study period should only be reported if the investigator suspects a causal relationship to study treatment.

AEs are coded using MedDRA terminology. The latest MedDRA version used for reporting will be specified in the CSR and as a footnote in the applicable tables/listings. AEs will be assessed according to the Common Terminology Criteria for Adverse Events (CTCAE) version 5.0 or current version.

AE summaries will include all AEs occurring during on-treatment period. All AEs collected in the AE (e)CRF page will be listed along with the information collected on those AEs e.g. AE relationship to study treatment, AE outcome etc. AEs with start date outside of on-treatment period will be flagged in the listings.

AEs will be summarized by number and percentage of subjects having at least one AE, having at least one AE in each primary system organ class and for each PT using MedDRA coding. A

Advanced Accelerator Applications,	Confidential
A Novartis company	
SAP amendment	

patient with multiple occurrences of an AE will be counted only once in the respective AE category. A subject with multiple CTCAE grades for the same PT will be summarized under the maximum CTCAE grade recorded for the event. AE with missing CTCAE grade will be included in the 'All grades' column of the summary tables.

In AE summaries, the primary SOC will be presented in order of descending frequency and the PT will be sorted within primary SOC in descending frequency.

The following AE summaries will be produced:

- Overview of AEs and deaths (number and % of subjects who died, with any AE, any SAE, any dose interruptions, etc)
- AEs by SOC and PT, summarized by relationship (all AEs and AEs related to study treatment), seriousness (SAEs and non-SAEs), leading to treatment discontinuation, leading to dose interruption, requiring additional therapy and leading to death.
- In addition, a summary of AEs with number of occurrences will be produced (an occurrence is defined as >1 day between start and prior end date of record of same PT).

For the legal requirements of ClinicalTrials.gov and EudraCT, two required tables, on AEs which are not SAEs with an incidence greater than 5% and on SAEs and SAEs suspected to be related to study treatment, will be provided by SOC and PT on the safety set population.

If for a same subject, several consecutive AEs (irrespective of study treatment causality, seriousness and severity) occurred with the same SOC and PT:

- a single occurrence will be counted if there is ≤ 1 day gap between the end date of the preceding AE and the start date of the consecutive AE.
- more than one occurrence will be counted if there is > 1 day gap between the end date of the preceding AE and the start date of the consecutive AE.

For occurrence, the presence of at least one SAE / SAE suspected to be related to study treatment / non-SAE has to be checked in a block e.g., among AEs in $a \le 1$ day gap block, if at least one SAE is occurring, then one occurrence is calculated for that SAE.

The number of deaths resulting from SAEs suspected to be related to study treatment and SAEs irrespective of study treatment relationship will be provided by SOC and PT.

AEs, AEs with suspected relationship to study treatment and SAEs will also be analysed for subgroups of interest described in Section 2.2.1.

